## **3. Analysis of Secondary Outcomes**

### ***3.1 Load force within session***

Descriptive statistics (Mean (SD)) of daily load symmetry will be reported. Within day comparisons of load force symmetry (mean of Baseline to same day Post

Training at each PT1, PT2, PT3, PT4) will be made using paired t tests (or Wilcoxon Signed Ranks tests) and reported with the appropriate t/Z statistic and p value. Effect sizes and 95% confidence intervals will also be calculated and reported in the final report. Results will also be presented graphically.

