Following these three visits of Pre-Test assessments, participants will return to complete five consecutive days of the training intervention. The intervention will consist of five consecutive days of TPAD training plus visual feedback training with a short over ground training (5-10 minutes) each day immediately following completion of treadmill based activities. After participants are readied for intervention, they will be assisted onto the treadmill and the treadmill will be initiated. Individuals will self-select gait speed with a physical therapist confirming speed is safe for the duration of training. Once gait speed is set, individuals will initiate five minutes of Baseline gait on the treadmill during which load force measures are recorded at minute 0-1 (BL1), minute 2-3 (BL2) and minute 4-5 (BL3). This Baseline gait will be followed by 40 minutes of tethered TPAD training with visual feedback provided. The amount visual feedback will be faded over the course of the five-day training. On completion of the tethered portion of training, participants will continue to ambulate on the treadmill for an additional 10 minutes during a Post-Training period. Measures of load force will be recorded during minute 0-1 (PT1), minute 3-4 (PT2), minute 6-7 (PT3) and minute 9-10 (PT4) of Post Training. Participants will then be assisted off the treadmill and an additional 5-10 minutes of over ground training will be conducted reinforcing weight shifting onto the paretic limb. Participants will be required to complete at least four days of training for data to be considered in the final analysis. Training sessions will last approximately 60 minutes (one hour) in duration.

On the fifth day of training, immediately following the final training session, participants will be allowed a 10-15 min seated rest break and over ground measures will be reassessed (Post

Test). All participants will be asked to return one week after completion of the intervention to undergo one final over ground assessment (Follow Up).

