**Assessed at each training visit at time points 3 and 5.**

Measures of load force will be taken while the participant is ambulating on the treadmill during both Baseline gait (at minute 0-1 (BL1), minute 2-3 (BL2) and minute 4-5 (BL3)) and Post Training (during minute 0-1 (PT1), minute 3-4 (PT2), minute 6-7 (PT3) and minute 9-10 (PT4)). This will be recorded via force plates embedded under the treadmill belts. The magnitude of force in the downward, vertical direction (z) and time the force was exerted on each force plate (for each the paretic and non paretic limb) will be extracted and used for analysis. These forces and times will be multiplied to yield an impulse force, and symmetry ratios will be calculated from the impulse of the load force.

$$\text{Impulse Force} = \text{Fmagnitude} * \text{Ftime}$$

$$\text{Force Symmetry} = \text{FzParetic}/\text{FzNon-paretic}$$

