## **Statistical Analyses**

Statistical assumptions and normality will be tested prior to running statistical analysis for measures of treatment tolerance, force symmetry, spatiotemporal gait parameters including stance symmetry and balance. A *p value* of 0.05 or lower will be considered statistically significant for all analyses.

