### ***3.2 Swing Symmetry Ratio***

Descriptive statistics (Mean (SD)) will be calculated and reported. Mean values of swing symmetry will be analyzed using repeated measures analysis of variance (ANOVA) to compare the mean of the pre-test measures to measures at post-test and follow up. Bonferonni corrections will be used to control for multiple comparisons. Effect sizes, and 95% confidence intervals will be calculated and reported with the F/Z statistic and p value. A graphical representation of the data will also be reported. Similar to stance symmetry, a linear regression model of daily change over time will be created using change scores from the mean of the three Pre Test measures to Day 1 of training. Within day changes for each of the five training days and changes from daily Pre Testing and from daily Post Testing will also be examined with a regression over time. Results of the regression models will be used to determine the presence of a significant change over the course of the intervention and will be reported with the corresponding slope.

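### The 20 within-day load symmetry tests (four windows on five days) each use 0.05 with no correction, although the SAP corrects families of at most three comparisons

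*SAP*

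**What the plan says.** SAP section 3.1 (Load force within session) plans "Within day comparisons of load force symmetry (mean of Baseline to same day Post" and continues "Training at each PT1, PT2, PT3, PT4) will be made using paired t tests", with Wilcoxon signed ranks tests as the alternative. Each result is to be "reported with the appropriate t/Z statistic and p value". Effect sizes, 95% confidence intervals, descriptive statistics and graphs are also promised.

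The windows are defined in SAP section 4.2.1: "minute 0-1 (PT1), minute 3-4 (PT2), minute 6-7 (PT3) and minute 9-10 (PT4"). The same section has load force assessed at every training visit. The text under the Trial Schema gives the number of visits: "The intervention will consist of five consecutive days of TPAD training plus visual feedback training".

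The opening of Statistical Analyses sets one threshold: a p value of "0.05 or lower will be considered statistically significant for all analyses". Section 3.1 does not modify it and does not label its tests exploratory.

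For the gait and balance outcomes (sections 2.2.2 and 3.2 to 3.8), the SAP compares the pre-test mean, post-test and follow-up by repeated measures ANOVA and adds that "Bonferonni corrections will be used to control for multiple comparisons".

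SAP section 2.3 under Efficacy classes within-day load change as a secondary measure. The primary load comparison (section 2.2.1) is separate: the Baseline mean on Day 1 against Post Training on Day 5.

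**The concern.** The SAP controls multiplicity where the family is small and leaves it uncontrolled where the family is largest. The four tests of one day also share a single Baseline mean. An unusually low Baseline on one day can therefore make several windows look like a gain at once, and they are not four separate pieces of evidence.

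The scientific question has two parts: does load symmetry rise within a session, and does that rise change over the five days? Neither part needs 20 verdicts. For the gait outcomes the SAP already regresses within-day change over time, but it specifies nothing comparable for load.

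At stake is how the secondary load results are read. They are listed as measures of preliminary force efficacy, and the Sample size justification says the study's results will be used to size larger trials. One or two significant windows among 20 could be reported as within-session learning or retention when they are chance.

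**Working it through.** The documents give no familywise error rate, power or sample size calculation for these tests, so there is no figure to reproduce.

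**Inputs from the documents**
- Windows per day: 4 (SAP 4.2.1). Training days: 5 (text under Trial Schema). Tests: 4 × 5 = 20.
- Threshold per test: 0.05 (Statistical Analyses).
- Participants: 12 enrolled, 10 expected to complete (protocol, Participants).
- Corrected families elsewhere: three time points, so at most 3 pairwise comparisons per outcome.

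**Inputs assumed**
- Sidedness is not stated. Two-sided tests are assumed, which puts 0.025 in the direction of a gain.
- Correlation among the 20 change scores is not given. It is varied from 0.25 to 0.9 within a day and from 0 to 0.5 between days. The lower end within a day follows from the shared Baseline. With three Baseline windows and independent window errors of variance 1, the Baseline mean has variance 1/3, each change has variance 1 + 1/3 = 4/3, and two changes share covariance 1/3. The correlation is (1/3)/(4/3) = 0.25.

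**Independent tests, no true effect**
- Any false significant result: 1 − 0.95^20 = 0.642. Expected number: 20 × 0.05 = 1.0.
- False gain: 1 − 0.975^20 = 0.397. Expected number: 20 × 0.025 = 0.5.
- For contrast, a family of 3 left uncorrected: 1 − 0.95^3 = 0.143.

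**Correlated tests** (simulated one-sample t tests on the changes, n = 10, normal data, no effect, 20,000 runs per row)

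| Within-day correlation | Between-day correlation | Any direction | Gain only |
|---|---|---|---|
| 0.25 | 0 | 0.628 | 0.378 |
| 0.5 | 0 | 0.585 | 0.342 |
| 0.7 | 0.3 | 0.480 | 0.249 |
| 0.8 | 0.5 | 0.383 | 0.195 |
| 0.9 | 0.5 | 0.334 | 0.167 |

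With n = 12 the results differ by about 0.01 or less. Even the last row is 0.334/0.05 = 6.7 times nominal for any result, and 0.167/0.025 = 6.7 times nominal for a gain.

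**Remedies**
- Bonferroni over 20: 0.05/20 = 0.0025 per test. Familywise error is 1 − 0.9975^20 = 0.049 if independent, and 0.031 to 0.050 in the simulations.
- Bonferroni over the four windows of one day only: 0.05/4 = 0.0125. This leaves 1 − 0.9875^20 = 0.222 across 20 independent tests, so correcting day by day is not enough.
- One paired test of each participant's averaged change: about 5% throughout, because it is a single test with one value per participant.

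**Window count.** The protocol's Treadmill Assessments section records Post Training force in minutes 1, 3, 5, 7 and 9, which is five windows against the SAP's four. The two should be reconciled. Five windows would make 25 tests: 1 − 0.95^25 = 0.723 for any direction and 1 − 0.975^25 = 0.469 for a gain, if independent.

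**The case against.** The strongest case for leaving the plan alone is that this is a secondary outcome in a small single-arm pilot. No rule in the SAP says that one significant window counts as efficacy. The Specific Objectives tie the overall conclusion to the primary load and stance questions plus feasibility. Section 3.1 already promises effect sizes and confidence intervals. Separate windows also serve a purpose, because the design asks whether load symmetry is retained after the tethers come off, and a fading effect would show in the sequence PT1 to PT4. All of this stands. It limits the consequence and argues for keeping the windows visible. It does not explain why these tests carry p values at 0.05, with neither a correction nor an exploratory label, when smaller families are corrected.

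A reader might infer two stronger points that the documents do not support.

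- **That a chance gain is more likely than not.** The 64% counts false results in either direction under independence. With two-sided tests a false gain reaches at most 40% with independent or positively correlated tests. It passes 50% only if the tests are one-sided at 0.05 and correlation is low (0.551 at correlations 0.5 and 0, but 0.272 at 0.9 and 0.5). The SAP states neither condition. Even the any-direction figure falls below 50% when the changes are strongly correlated.
- **That the planned tests waste power.** A pooled test can be shown to beat Bonferroni over 20, but the SAP does not plan Bonferroni over 20, so that comparison says nothing about the plan. The result would also depend on an assumed effect pattern.

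**Conclusion.** The point holds as a matter of multiplicity in a secondary analysis. The count of 20, the 0.05 threshold, the absence of any correction in section 3.1 and the contrast with the corrected gait outcomes all come directly from the SAP and need no assumption.

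The size does need assumptions. With no true within-session effect, two-sided tests and independent or positively correlated changes, the chance of at least one false significant result is up to 64%, and of a false gain up to 40%. Over the assumed correlations the ranges are about 33% to 63% and 17% to 38%. The nominal level is 5% for any result, or 2.5% in the direction of a gain. The true position within these ranges cannot be fixed from the documents.

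The primary Day 1 to Day 5 load comparison is not affected. This is a change that should be made because it is cheap, not one on which the trial's main conclusions depend.

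**What to change.** Rewrite SAP section 3.1 as follows.

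1. **Main within-session test.** For each participant, compute the mean Post Training minus Baseline load symmetry on each day, average over windows and days, and apply one paired t test (or Wilcoxon test) at 0.05. State that it is two-sided. Participants with four of the five days, whom the SAP keeps in the analysis, contribute the days they have.
2. **Trend over days.** Fit a slope of daily change on day for each participant and apply one t test to the slopes.
3. **Windows.** Show PT1 to PT4 by day as estimates with 95% confidence intervals and a graph, and make no significance claims.
4. **If the 20 tests are kept,** apply Holm across all 20, so that the smallest p value is compared with 0.05/20 = 0.0025.

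If a mixed model is preferred, it needs a participant-level random phase effect (Baseline against Post Training) and must account for day. A random intercept alone is not adequate because it treats repeated windows as independent evidence on phase. Under no effect, with n = 10, three Baseline and four Post Training windows and five days, its phase test rejected about 14% to 25% of the time when participants' within-session response was assumed to have an SD of 0.3 to 0.5 of the window SD.

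The cost is SAP wording and two simple tests, with no extra data. The drawbacks are that fewer single windows will be labelled significant, and that averaging can dilute an effect confined to some windows or days. The estimates in item 3 keep such a pattern visible.

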### ***3.2 Swing Symmetry Ratio***

Descriptive statistics (Mean (SD)) will be calculated and reported. Mean values of swing symmetry will be analyzed using repeated measures analysis of variance (ANOVA) to compare the mean of the pre-test measures to measures at post-test and follow up. Bonferonni corrections will be used to control for multiple comparisons. Effect sizes, and 95% confidence intervals will be calculated and reported with the F/Z statistic and p value. A graphical representation of the data will also be reported. Similar to stance symmetry, a linear regression model of daily change over time will be created using change scores from the mean of the three Pre Test measures to Day 1 of training. Within day changes for each of the five training days and changes from daily Pre Testing and from daily Post Testing will also be examined with a regression over time. Results of the regression models will be used to determine the presence of a significant change over the course of the intervention and will be reported with the corresponding slope.

### ***3.3 Percentage of Time in Double Support***

Descriptive statistics (Mean (SD)) will be calculated and reported. Mean values of time in Double Support during the gait cycle will be analyzed using repeated measures analysis of variance (ANOVA) to compare the mean of the pre-test measures to measures at post-test and follow up. Bonferonni corrections will be used to control for multiple

comparisons. Effect sizes, and 95% confidence intervals will be calculated and reported with the F/Z statistic and p value. A graphical representation of the data will also be reported. Similar to stance and swing symmetry, a linear regression model of daily change over time will be created using change scores from the mean of the three Pre Test measures to Day 1 of training. Within day changes for each of the five training days and changes from daily Pre Testing and from daily Post Testing will also be examined with a regression over time. Results of the regression models will be used to determine the presence of a significant change over the course of the intervention and will be reported with the corresponding slope.

### ***3.4 Stride Length Symmetry Ratio***

Descriptive statistics (Mean (SD)) will be calculated and reported. Mean values of Stride Length Symmetry ratios will be analyzed using repeated measures analysis of variance (ANOVA) to compare to compare the mean of the pre-test measures to measures at post-test and follow up. Bonferonni corrections will be used to control for multiple comparisons. Effect sizes, and 95% confidence intervals will be calculated and reported with the F/Z statistic and p value. A graphical representation of the data will also be reported. Similar to stance and swing symmetry and double limb support, a linear regression model of daily change over time will be created using change scores from the mean of the three Pre Test measures to Day 1 of training. Within day changes for each of the five training days and changes from daily Pre Testing and from daily Post Testing will also be examined with a regression over time. Results of the regression models will

be used to determine the presence of a significant change over the course of the intervention and will be reported with the corresponding slope.

### ***3.5 Stride Length***

Descriptive statistics (Mean (SD)) will be calculated and reported. Mean values of Stride Length will be analyzed using repeated measures analysis of variance (ANOVA) to compare to compare the mean of the pre-test measures to measures at post-test and follow up. Bonferonni corrections will be used to control for multiple comparisons. Effect sizes, and 95% confidence intervals will be calculated and reported with the F/Z statistic and p value. A graphical representation of the data will also be reported. Similar to stance and swing symmetry and double limb support, a linear regression model of daily change over time will be created using change scores from the mean of the three Pre Test measures to Day 1 of training. Within day changes for each of the five training days and changes from daily Pre Testing and from daily Post Testing will also be examined with a regression over time. Results of the regression models will be used to determine the presence of a significant change over the course of the intervention and will be reported with the corresponding slope.

### ***3.6 Stride Velocity***

Descriptive statistics (Mean (SD)) will be calculated and reported. Mean values of Stride Velocity will be analyzed using repeated measures analysis of variance (ANOVA) to compare to compare the mean of the pre-test measures to measures at post-test and follow up. Bonferonni corrections will be used to control for multiple comparisons. Effect sizes, and 95% confidence intervals will be calculated and reported

with the F/Z statistic and p value. A graphical representation of the data will also be reported. Similar to stance and swing symmetry and double limb support, a linear regression model of daily change over time will be created using change scores from the mean of the three Pre Test measures to Day 1 of training. Within day changes for each of the five training days and changes from daily Pre Testing and from daily Post Testing will also be examined with a regression over time. Results of the regression models will be used to determine the presence of a significant change over the course of the intervention and will be reported with the corresponding slope.

### ***3.7 Gait Velocity***

Descriptive statistics (Mean (SD)) will be calculated and reported. Mean values of Stride Length Symmetry ratios will be analyzed using repeated measures analysis of variance (ANOVA) to compare to compare the mean of the pre-test measures to measures at post-test and follow up. Bonferonni corrections will be used to control for multiple comparisons. Effect sizes, and 95% confidence intervals will be calculated and reported with the F/Z statistic and p value. A graphical representation of the data will also be reported. Similar to stance and swing symmetry and double limb support, a linear regression model of daily change over time will be created using change scores from the mean of the three Pre Test measures to Day 1 of training. Within day changes for each of the five training days and changes from daily Pre Testing and from daily Post Testing will also be examined with a regression over time. Results of the regression models will be used to determine the presence of a significant change over the course of the intervention and will be reported with the corresponding slope.

### **3.8 Balance**

Descriptive statistics (Mean (SD)) will be calculated and reported. Mean values of raw scores on the BBS will be analyzed using repeated measures analysis of variance (ANOVA) to compare the mean of Pre-Test measures to measures at Post Test and Follow Up also using a repeated measures ANOVA. The F value and statistical significance will be reported. A graphical representation of the data will also be reported. Effect sizes and 95% confidence intervals will also be calculated and included in the final report. Descriptive statistics (Mean (SD)) will be calculated and reported. Mean values of Stride Length Symmetry ratios will be analyzed using repeated measures analysis of variance (ANOVA) to compare to compare the mean of the pre-test measures to measures at post-test and follow up. Bonferonni corrections will be used to control for multiple comparisons. Effect sizes, and 95% confidence intervals will be calculated and reported with the F/Z statistic and p value. A graphical representation of the data will also be reported. Similar to stance and swing symmetry and double limb support, a linear regression model of daily change over time will be created using change scores from the mean of the three Pre Test measures to Day 1 of training. Within day changes for each of the five training days and changes from daily Pre Testing and from daily Post Testing will also be examined with a regression over time. Results of the regression models will be used to determine the presence of a significant change over the course of the intervention and will be reported with the corresponding slope.

